3.2 Double-Blind Treatment Period

Double-Blind Treatment Period (for all randomized patients)

- Patients who fulfil the randomization criteria and do not meet any of the withdrawal criteria during the Open Label Period or at the time of randomization will be randomly assigned via a centralized randomization system to receive vortioxetine or placebo in a 1:1 ratio. Randomization will be stratified by patient inclusion sources (*de novo* patients, rollover patients from 12709A, or from 12712A).
- Patients randomized to vortioxetine will continue on their final dose from the Open Label Period or the dose they had on their last visit in Study 12712A, as applicable.
- The maximum duration of the Double-Blind Treatment Period will be 26 weeks.
- Patients who relapse during the Double-Blind Treatment Period must be withdrawn from the study. The criterion for a relapse is a CDRS-R total score of ≥ 40 with a history of 2 weeks of clinical deterioration, or a clinical deterioration that in the investigator's opinion warrants alteration of treatment to prevent full relapse.

A Safety Follow-up Visit will be performed 4 weeks after withdrawal or completion of the Double-Blind Treatment Period.

Panel 2 Schedule of Study Design

* Patients in remission (CDRS total score ≤ 28) at the two last visits in the Open Label period / Study 12712A OR with an adequate clinical response ($\geq 50\%$ reduction in the CDRS-R total score compared to the baseline score and a CDRS-R total score ≤ 35) at the two last visits in the Open Label period

**Relapse: CDRS-R total score of ≥ 40 with a history of 2 weeks of clinical deterioration, or a clinical deterioration that in the investigator's opinion warrants alteration of treatment to prevent full relapse

4 Definitions

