11.6 Pharmacokinetic Analyses

The pharmacokinetic analyses will be described in a separate population PK analysis plan.

12 Safety

The safety analyses will be performed for each period, based on the APES and the APRS. Unless otherwise specified the tables and listings of the Open Label Period are based on APES. The tables and listings of the Double-Blind Treatment Period are based on the APRS.

All safety endpoints will be reported for the 12-week Open Label Period and the 26-week Double-Blind Treatment Period separately. The results of the safety analysis of the Open Label Period will be presented by patient group (*de novo* patients and rollover patients from Study 12709A) and overall.

The results of the safety analyses of the Double-Blind Treatment Period will be displayed by treatment group and overall.

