12.1.4 Allocation of TEAEs to Treatment Periods

TEAEs will be allocated to treatment periods according to the time of onset of the adverse event:

Pre-treatment AEs – an adverse event that starts on or after the date the patient signed the Informed Consent Form and prior to the date of first dose of IMP in Open Label Period. This definition will only be used for *de novo* patients.

TEAE in the Open Label Period – an AE that starts on or after the date of the first IMP intake in the Open Label Period and before the date of the end of Open Label Period. In addition, for *de novo* patients only, this also includes AEs that start before the date of the start of Open Label Period and worsens before the date of the end of the Open Label Period.

TEAE in the Double-Blind Treatment Period – a TEAE that starts on or after the date of the first IMP intake in the Double-Blind Treatment Period and before the date of the end of Double-Blind Treatment Period, **OR** starts before the date of the start of Double-Blind Treatment Period and worsens on or after the date of the first IMP intake in the DB treatment period and before the date of the end of the Double-Blind Treatment Period

TEAE in the Safety Follow-up Period – an AE that starts on or after the date of the end of Double-Blind Treatment Period or on or after the date of withdrawal (in either the Open Label Period or the Double-Blind Treatment Period).

Adverse events that are ongoing in either parent study at the time of entry into the current study will be included in the present study. All data will be transcribed and the rules as described above will apply.

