12.1.9 Presentation of Serious Adverse Events

All the SAEs will be listed for the APES in the Open Label Period and for the APRS in the Double-Blind Treatment Period.

Treatment-emergent SAEs will be summarized for each treatment period by:

- SOC and preferred term
- Preferred term

A listing presenting all SAEs will be prepared.

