12.5.2 General Behavior Inventory (GBI) 10-Item Mania Scale

The GBI 10-item mania scale is a parent- and patient-rated scale designed to screen for manic symptoms in children and adolescents. The ten items are rated on a 4-point scale from 0 (never or hardly ever) to 3 (very often or almost constantly). The total score ranges from 0 to 30, with higher scores indicating greater pathology. Only the parent-rated scale will be used in this study.

Summary statistics on the total score, absolute scores as well as changes from baseline for each visit as well as the latest assessment will be presented per study period and inclusion source (Open Label Period) and treatment group (Double-Blind Treatment Period).

13 Interim Analyses

No interim analyses will be performed.

14 Sample Size Considerations

The calculation of power is based on a log-rank test for the time to relapse at a one-sided 5% level of significance using SAS Proc Power. A sample size of 80 randomized patients (40 patients per treatment group) will provide at least 80% power to find a difference between vortioxetine and placebo as statistically significant, when expecting cumulative relapse rates at 0.42 and 0.69 over 26 weeks, respectively corresponding to a hazard-ratio of 2.15. The assumption of relapse rates (42% and 69% over 6 months for vortioxetine and placebo, respectively) is based on observed rates from a similarly designed relapse-prevention study of fluoxetine in pediatric patients with MDD who had an adequate response after 12 weeks of acute treatment¹.

It is anticipated that approximately 60% of *de novo* patients enrolled into the Open Label Period will qualify for the Double-Blind Treatment Period. To achieve 80 randomized patients, 150 patients are estimated to be enrolled into the study (depending on number and randomization rate of *de novo* and rollover patients).

15 Statistical Software

The statistical software used will be SAS[®], Version 9.4 or later.

16 Details on Data Handling

An LOCF approach will be used for the Double-Blind Treatment Period of the following scales: CDRS-R, PQ-LES-Q, CGI-I and CGI-S.

The LOCF approach will only be used for the total scores (if applicable). The last usable assessment in the Double-Blind Treatment Period (excluding the randomization assessment) will be used to impute missing values for the LOCF. See also section [Section 16.1.3](#) for the handling of missing data related to COVID-19.

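### SAEs starting on or after double-blind exit are assigned to a Safety Follow-up category for which the SAP names no by-arm table, so only listings are certain to show them

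*SAP*

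**What the plan says.** **Allocation.** Under SAP 4.2, a withdrawn child's double-blind period ends at the withdrawal visit. Under SAP 12.1.4, a double-blind TEAE must start or worsen before the date that period ends. The Safety Follow-up category takes "an AE that starts on or after the date of the end of Double-Blind Treatment Period or on or after the date of withdrawal", and it covers withdrawal from either period.

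**Reporting.** SAP section 12 states: "All safety endpoints will be reported for the 12-week Open Label Period and the 26-week Double-Blind Treatment Period separately". Section 12.2 repeats this for the other safety data. The adverse event overview (12.1.5) is promised for each period, but an analysis set is given only for Open Label (APES) and Double-Blind (APRS). The TEAE tables (12.1.7) name the same two. For serious events, 12.1.9 says: "All the SAEs will be listed for the APES in the Open Label Period and for the APRS in the Double-Blind Treatment Period". It then promises treatment-emergent SAE tables per treatment period, without saying which periods count, and a listing of all SAEs.

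**Collection.** Protocol 8.6 gives capture of SAEs as a purpose of the follow-up contact. Footnote f of Protocol Panel 3 limits that contact to adverse events still ongoing and new SAEs. The C-SSRS is not scheduled there.

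**Exit.** SAP 3.2: "Patients who relapse during the Double-Blind Treatment Period must be withdrawn from the study".

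**The concern.** The plan collects SAEs after double-blind exit, gives them their own category, and then names neither an analysis set nor a table for it. A reader comparing serious events between arms would have the double-blind tables and would have to count the rest from listings.

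The design makes this more than a formality. In a relapse-prevention trial where relapse ends participation, the weeks after exit are a substantial part of what is observed after randomization, and more placebo than vortioxetine children are expected to enter them through relapse. Because the C-SSRS is not scheduled at the follow-up contact, SAE reports are the main record of suicidality in that window.

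The boundary matters too. Protocol 5.5 requires withdrawal from treatment for a positive answer to C-SSRS ideation question 4 or 5, and Protocol 9.4.10 asks for a corresponding SAE. If that SAE and the end of the period carry the same date, 12.1.4 assigns the event that led to the exit to follow-up.

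**Working it through.** **1. The plan's own figure.** SAP section 14 (same text in Protocol 16.10) gives the test "at a one-sided 5% level of significance using SAS Proc Power", and says: "A sample size of 80 randomized patients (40 patients per treatment group) will provide at least 80% power", "expecting cumulative relapse rates at 0.42 and 0.69 over 26 weeks, respectively corresponding to a hazard-ratio of 2.15". Allocation is 1:1 (SAP 3.2).

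- Hazard ratio: ln(1 − 0.69) / ln(1 − 0.42) = 2.150. This agrees.
- Expected relapses: 40 × 0.42 = 16.8 and 40 × 0.69 = 27.6, total 44.4.
- Schoenfeld power, one-sided 5%: Φ(√(44.4 × 0.25) × ln 2.15 − 1.645) = Φ(0.905) = 81.7%. A simulated log-rank test gives 80.9%. The stated power reproduces and is not in dispute.

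**2. How many leave at relapse.** 44.4 / 80 = 55.5% of randomized children. Of the roughly 150 enrolled it is 44.4 / 150 = 29.6%, so the statement applies to randomized children only.

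**3. Other dropout.** The documents give no rate, so I assume 0% to 40% over 26 weeks. With relapse hazard h = −ln(1 − p)/26 and dropout hazard k = −ln(1 − d)/26, the share leaving at relapse is h/(h + k) × (1 − exp(−26(h + k))), and the share leaving early for any reason is 1 − exp(−26(h + k)). The percentages are averaged over the two arms.

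| Other dropout | Relapse exits, vortioxetine / placebo | Relapse exits, % of 80 | All early exits, % of 80 |
|---|---|---|---|
| 0% | 16.8 / 27.6 | 55.5 | 55.5 |
| 10% | 16.0 / 26.5 | 53.1 | 59.9 |
| 20% | 15.2 / 25.3 | 50.6 | 64.4 |
| 25% | 14.8 / 24.6 | 49.3 | 66.6 |
| 40% | 13.5 / 22.7 | 45.2 | 73.3 |

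Relapse exits alone fall below half at about 25% other dropout. All early exits stay above half throughout.

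**4. Size of the window.** Assume no other dropout, exponential relapse times and a full 4 weeks of follow-up per child.

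- Mean double-blind time is p/h: 20.05 weeks on vortioxetine and 15.32 on placebo. Times 40, that is 801.9 + 612.7 = 1,414.6 patient-weeks.
- Follow-up is 80 × 4 = 320 patient-weeks, or 320 / (320 + 1,414.6) = 18% of post-randomization observation.
- The part after a relapse is 16.8 × 4 = 67.2 on vortioxetine and 27.6 × 4 = 110.4 on placebo, total 177.6.

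Total follow-up is equal by arm (160 each); only the post-relapse part differs. These are upper figures, because SAP 4.2 counts the 4 weeks from last intake while the double-blind period runs to the withdrawal visit.

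**5. The cut-off.** SAP 4.2 starts Safety Follow-up at the last intake of study drug. SAP 12.1.4 starts it at the end of the double-blind period or at withdrawal. If the last dose precedes the withdrawal visit, the days between belong to both periods under 4.2. If the withdrawal date precedes the visit, an event between the two meets both definitions in 12.1.4. If the two dates coincide, an event starting that day is follow-up only.

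**The case against.** The strongest reply is that the SAP does not exclude follow-up from its tables. Section 4.2 defines Safety Follow-up as a period, and 12.1.4 lists it under a heading about treatment periods. The SAE summary in 12.1.9 is per treatment period, and the analysis sets in that section are attached to the listing sentence, not to the summary. The TEAE definition in 12.1.3 has no end date. Table templates are kept in a separate document (SAP section 1). This stands as far as 12.1.9 goes: the text is ambiguous there. It does not settle the matter, because section 12, the overview's analysis sets and 12.1.7 name two periods only.

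The events are also not lost. Listings carry treatment group (SAP section 6), the adverse event listing shows the period of onset (12.1.5), 12.5.1 adds a listing with suicidality SAEs, and the DMC sees unblinded safety data (Protocol 10.6.1). All of that is right. With 40 children per arm, a count could be made by hand. What is missing is a planned one.

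Four stronger readings are tempting and lack support:

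- *Deaths go uncounted.* The 12.1.5 overview counts patients who die in the course of the study, and Protocol 8.7 ends a patient's study at the last planned contact. A follow-up death may therefore already enter the by-arm overview.
- *Relapsers are the group most likely to have serious events.* That is a clinical inference which the documents do not make.
- *Drug remains on board for about two weeks.* The 66-hour half-life in Protocol 1.1.3.1 is an adult figure, and no paediatric one is given.
- *Open-label withdrawals would contaminate an arm comparison.* They share a label in 12.1.4, but they are not in the APRS, and no table pools them.

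**Conclusion.** The point holds as a gap in specified reporting. Following the SAP's text, SAEs that start after double-blind exit, and some dated on the exit day itself, are certain to be listed but not certain to be counted by arm. On the plan's rates about 44 of 80 randomized children exit at relapse (42% against 69%), and follow-up makes up about 18% of post-randomization observation. Both figures assume little other dropout, and the second also assumes exponential relapse times and a full 4 weeks per child.

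A reader might infer that SAE incidence by arm is understated. The documents do not support that as a finding: they give no SAE rate, and the double-blind tables describe the double-blind window, in which an SAE starting before the end date already counts. The primary endpoint and its analysis are unaffected.

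**What to change.** In SAP 12.1.5 and 12.1.9:

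- Add a summary by treatment group on the APRS of SAEs, including suicidality SAEs, with onset from the first double-blind dose through the Safety Follow-up contact. Show events with follow-up onset in a separate column.
- State that deaths are counted through the same contact.
- Summarize follow-up SAEs of open-label withdrawals separately on the APES.

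In SAP 4.2 and 12.1.4:

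- Use one cut-off between the double-blind and follow-up periods, and count events starting on the withdrawal date in the double-blind period.

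The cost is one or two extra tables from data already collected. Protocol 8.1 places children on usual clinical care after withdrawal, so the follow-up column mixes the randomized treatment's aftermath with later care. It should be interpreted separately from the double-blind column.

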12.1.5 Presentation of Adverse Events

All adverse events will be listed for the APES and APRS for the Open Label Period and the Double-Blind Treatment Period, including a flag for TEAEs. The period in which the AE started will be displayed.

For each period, an overview of the number and percentage of patients with TEAEs, serious adverse events (SAEs), or adverse events leading to withdrawal and patients who died during the study will be provided.

This overview will be based on the APES for the Open Label Period and APRS for the Double-Blind Treatment Period. For TEAEs, SAEs, and adverse events leading to withdrawal, the total number of events will be included.

12.1.6 Presentation of Pre-treatment Adverse Events

Pre-treatment adverse events will be summarized by preferred term based on APES.

12.1.7 Presentation of Treatment-emergent Adverse Events

The following summaries will be provided for the Open Label Period (based on the APES) and for the Double-Blind Treatment Period (based on the APRS) separately:

- TEAEs by SOC and preferred term
- TEAEs by preferred term
- TEAEs with an incidence $\geq 5\%$ by preferred term

- Causally related TEAEs by SOC and preferred term
- TEAEs by intensity (*mild/moderate/severe*), SOC, and preferred term
- Causally related TEAEs by intensity, SOC, and preferred term

12.1.8 Presentation of Deaths

All the adverse events in patients who died during the study will be listed for the APES in the Open Label Period and for the APRS in the Double-Blind Treatment Period.

12.1.9 Presentation of Serious Adverse Events

All the SAEs will be listed for the APES in the Open Label Period and for the APRS in the Double-Blind Treatment Period.

Treatment-emergent SAEs will be summarized for each treatment period by:

- SOC and preferred term
- Preferred term

A listing presenting all SAEs will be prepared.

12.1.10 Presentation of Adverse Events Leading to Withdrawal

All the adverse events leading to withdrawal will be listed. TEAEs leading to withdrawal will be summarized per treatment period by:

- SOC and preferred term
- Preferred term

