7.2 Withdrawals

The number of patients who withdrew from the Open Label Period will be summarized by *de novo* patients, rollover patients from Study 12709A and total. The number of patients who withdrew from the Double-Blind Treatment Period will be summarized by treatment group and total. The primary reason for withdrawal as well as all reasons for withdrawal will be presented per period.

Patients who withdrew from the study will be listed and the listing will include the number of days in the study until withdrawal from the study, the number of days on IMP, the primary reason for withdrawal, and all reasons for withdrawal.

8 Demographics and Baseline Characteristics

Summary tables on demographic and baseline characteristics will be presented for both the Open Label Period and the Double-Blind Treatment Period separately. The baseline characteristics for the Open Label Period will be based on the APES and will be presented for *de novo* patients, rollover patients (from Study 12709A) and overall.

For the Double-Blind Treatment Period the summary tables on demographics will be based on the FAS and results will be presented per treatment group (vortioxetine and placebo) and in total.

Demographics (sex, age, ethnicity and race), baseline characteristics (height, weight and BMI), disease characteristics and baseline efficacy variables will be summarized.

The following baseline (randomization) efficacy variables will be summarized:

CDRS-R total score

CGI-S score

PQ-LES-Q scores (total score and overall score (item 15))

Disease characteristics will include MDE history (MDD history, including number of MDEs, duration of current episode, treatment type (psychotherapy / pharmacotherapy) for MDD. In addition, MDD treatment will be summarized.

Medical history from the Medical History eCRF page will be coded with medical dictionary for regulatory activities (MedDRA) version 19.0 or above. All medical histories, data on major depressive disorder history and treatment, the family psychiatric history and the history of stimulant medication will be listed.

9 Recent and Concomitant Medication

Recent and concomitant medication will be coded using the WHO Drug Dictionary (WHO Global B3 Mar 2020).

Medications will be classified according to the start and stop time and summarized by anatomical therapeutic chemical (ATC) code, generic drug name:

- medication discontinued prior to first dose of IMP in Open Label Period

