12.1.3 Classification of Adverse Events

Adverse events will be classified according to the time of onset of the adverse event:

- *pre-treatment adverse event* – an adverse event that starts on or after the date the patient signed the *Informed Consent Form* and prior to the date of first dose of IMP. As such, this definition will only be used for *de novo* patients.
- *treatment-emergent adverse event (TEAE)* – *an adverse event that starts or increases in intensity and/or seriousness on or after the date of first dose of IMP*

Adverse events, sorted by system organ class (SOC) and preferred term, will be summarized by treatment group.

An adverse event is considered causally related to the use of the IMP when the causality assessment by the investigator is *probable* or *possible*. For pre-treatment adverse events, a causality assessment is not relevant.

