16.3.2 Changes in Intensity or Seriousness of Adverse Events

Changes in adverse event intensity or seriousness are recorded on multiple rows in the dataset. When classifying adverse events into periods, an event will be assigned to more than one period only if the intensity increases or if a non-serious event becomes serious. An adverse event that changes in intensity or seriousness in a period will contribute to the count of events as a single event.

In summaries of adverse events presented by intensity, the maximum intensity of the adverse event will be used. The maximum intensity is searched for in events with changes, as well as over repeated events based on the preferred term. Adverse events for which information on intensity is missing will be classified as *severe*.

Adverse events for which information on seriousness is missing will be classified as *serious*.

References

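### The by-arm table of adverse events leading to double-blind withdrawal can miss withdrawals whose event began earlier and did not worsen, and so disagree with the disposition table

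*SAP*

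**What the plan says.** - **Withdrawal table, SAP 12.1.10.** All adverse events (AEs) leading to withdrawal are listed. For the tables, "TEAEs leading to withdrawal will be summarized per treatment period by" system organ class and preferred term. No allocation rule is given here.
- **Allocation rule, SAP 12.1.4.** "TEAEs will be allocated to treatment periods according to the time of onset of the adverse event". One exception applies to the double-blind period: an event also belongs there if it "starts before the date of the start of Double-Blind Treatment Period and worsens on or after the date of the first IMP intake" in that period. An event starting on or after the date of withdrawal is allocated to Safety Follow-up.
- **Second period, SAP 16.3.2.** "an event will be assigned to more than one period only if the intensity increases or if a non-serious event becomes serious".
- **Definition of a treatment-emergent AE (TEAE), SAP 12.1.3.** "an adverse event that starts or increases in intensity and/or seriousness on or after the date of first dose of IMP".
- **Carried-over events, SAP 12.1.4.** "Adverse events that are ongoing in either parent study at the time of entry into the current study will be included", and the same allocation rules apply to them.
- **Disposition, SAP 7.2.** "The number of patients who withdrew from the Double-Blind Treatment Period will be summarized by treatment group and total". Primary and all reasons for withdrawal are given per period.
- **Overview, SAP 12.1.5.** A per-period overview counts patients with AEs leading to withdrawal. They are named separately from TEAEs, again without a rule for choosing the period.

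**The concern.** Withdrawal is a dated event, and its period is known for every child. A table of AEs leading to withdrawal is read as showing why children stopped in that period. Under an onset rule it instead shows events that began, or worsened, in that period and led to withdrawal at some point.

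The two differ in this design because every randomized child has already taken vortioxetine, either in the open-label period or in Study 12712A. An event can start before randomization, persist unchanged, and lead to withdrawal after it. The double-blind table is the randomized, by-arm summary of which events led to stopping, and it would leave that child out. The open-label table would meanwhile show an AE withdrawal for a child who completed that period and was randomized. With about 40 children per arm, one or two such cases would visibly change the comparison.

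**Working it through.** **Step 1: follow the rules for a child withdrawn in the double-blind period because of an AE.** SAP 7.2 counts the child as a double-blind withdrawal in every row.

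| Event that led to withdrawal | Period under SAP 12.1.4 and 16.3.2 | In the double-blind table of 12.1.10? |
|---|---|---|
| Starts on double-blind treatment, before that period ends | Double-blind | Yes |
| Starts in the open-label period, then worsens or becomes serious on double-blind treatment | Open-label and double-blind | Yes |
| Starts in the open-label period, unchanged | Open-label only | No; it is in the open-label table |
| Starts in a parent study, unchanged | Not a TEAE in any period | No; in no TEAE-withdrawal table |
| Starts before first dose in a *de novo* patient, unchanged | Pre-treatment | No; in no TEAE-withdrawal table |
| Starts on the date of withdrawal | Safety Follow-up | No |

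For the last row, SAP 4.2 ends the double-blind period at the withdrawal visit, and a double-blind TEAE must start before that end. If the visit is on the withdrawal date, the event goes to Safety Follow-up only. If the visit is later, the event meets both definitions and the SAP does not say which prevails. SAP 12 and 12.1.7 specify summaries for the open-label and double-blind periods only.

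**Step 2: size per child.** The documents give no rate of AE withdrawal, so there is no planned figure to reproduce. SAP 14 plans 40 patients per arm, so one missed child is 1/40 = 2.5 percentage points. If an arm has 2 to 4 AE withdrawals (assumed), one missed child is 1/2 = 50% to 1/4 = 25% of that arm's count.

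**Step 3: effect on the comparison between arms.** Let V and P be the true AE withdrawals on vortioxetine and placebo, and eV and eP those the table misses.

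- True difference = (V − P)/40
- Difference shown = ((V − eV) − (P − eP))/40
- Error = −(eV − eP)/40

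With assumed counts V = 4 and P = 2, the true difference is 2/40 = +5.0 points.

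| Missed (eV, eP) | Counts shown | Difference shown |
|---|---|---|
| (1, 0) | 3 v 2 | +2.5 |
| (2, 0) | 2 v 2 | 0.0 |
| (2, 1) | 2 v 1 | +2.5 |
| (1, 1) | 3 v 1 | +5.0 |
| (0, 1) | 4 v 1 | +7.5 |

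The sign of the error depends only on eV − eP, which the documents do not give. Allocation by period of withdrawal makes eV = eP = 0 and returns +5.0 in every row.

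**The case against.** **The SAP is silent here, and the onset reading is an inference.** It is true that 12.1.10 does not say which period it means. But the table is a table of TEAEs, and 12.1.4 is the only rule placing TEAEs in periods. A programmer following the SAP would apply it.

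**Earlier-onset events are not all lost.** This stands. A reader might infer that any event starting before randomization is excluded. It is not: events that worsen or become serious on double-blind treatment are counted there. Only unchanged events, and those starting on the withdrawal date, are affected.

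**The withdrawals are reported elsewhere.** This also stands. A reader might take the 12.1.10 table to be the only randomized comparison of treatment stopping. SAP 7.2 gives withdrawals by arm with reasons per period, every AE leading to withdrawal is listed, and the 12.1.5 overview is not limited to TEAEs, so it could include them. What is lost is the by-arm breakdown by organ class and preferred term, and its agreement with 7.2.

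**The case should be uncommon.** This is fair. Protocol 3.2 describes the randomized patients as those who tolerate and respond to the drug, and the dose is fixed from Week 8 of the open-label period. The child must carry an event into randomization and then stop for it without recorded worsening. That argues for a small number, but at 40 per arm a small number is enough to matter.

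**Allocation by withdrawal has its own cost.** The table would no longer be a strict subset of the double-blind TEAE tables. That is true, and a footnote flag deals with it.

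**Conclusion.** The concern holds in a limited form. Followed as written, the SAP can omit from the by-arm double-blind table a withdrawal caused by an event that began earlier and neither worsened nor became serious, or that began on the date of withdrawal. The table can then disagree with 7.2. Each such child is 2.5 percentage points of an arm at the planned size. The number of such children is unknown, and the illustrations above rest on assumed counts.

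A reader might infer that the rule undercounts vortioxetine. The documents do not support that. Both arms had vortioxetine before randomization, the rule is identical in both, and no rates of persistence or withdrawal are given by arm. A larger loss on vortioxetine is plausible if persisting events ease after the switch to placebo, but that is an assumption. Losing one placebo case would make vortioxetine look worse.

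No efficacy analysis is affected. The correction is worth making because the count would be wrong under a rule the SAP itself states, and the data to put it right are already collected.

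**What to change.** Add to SAP 12.1.5 and 12.1.10, before unblinding:

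> AEs leading to withdrawal are tabulated in the period in which the patient was withdrawn, as in section 7.2, whatever the period of onset and whether or not the event is treatment-emergent.

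Then:

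- Retitle the 12.1.10 table as AEs, not TEAEs, leading to withdrawal.
- Flag with a footnote any event that is not a double-blind TEAE.
- Reconcile the AE-withdrawal counts with 7.2, by arm and period.
- Keep onset-based allocation for all other TEAE tables.

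The cost is one sentence in each of the two sections and a change to the table program, with no new data. The remaining downside is that the withdrawal table is no longer a strict subset of the double-blind TEAE tables, which the flag makes visible.
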